## **12.9 Protocol Deviations and Violations**

Exceptions to the eligibility criteria will not be granted. It is expected that subjects will meet all eligibility criteria. Departures from the protocol should be avoided, unless required for the safety of the subject. Should other unexpected circumstances arise that will require deviation from protocol-specific procedures, the investigator should contact the Sponsor to discuss the appropriate course of action.

The investigator should document all protocol deviations/violations in the subject's CRF and source documents or the investigator Site File, if appropriate. Protocol deviations will be documented by the clinical trial monitor and will be included in the final clinical trial report. Protocol deviations should be submitted to IRB/REB/IEC, in accordance with the site's IRB/REB/IEC requirements.

## **12.10 Amendments to the Protocol**

To alter the protocol, amendments must be written by the Sponsor and approvals must be received from all parties that approved the original protocol (IRB/REB/IEC, and if applicable, the local regulatory authorities) before implementation. Notwithstanding the need for approval of formal protocol amendments, the investigator is expected to take any immediate action required for the safety of any subject included in the clinical trial, even if this action represents a deviation from the protocol.

The Sponsor may make administrative changes (i.e., changes that do not significantly affect subject safety, the clinical trial's scope or scientific quality) without a formal protocol amendment.

## **12.11 Discontinuation of the Clinical Trial**

The Sponsor reserves the right to discontinue the clinical trial under the conditions specified in the clinical trial agreement.

## **12.12 Investigator Responsibilities**

The investigator(s) should be qualified by education, training, and experience to assume responsibility for the proper conduct of the clinical trial, should meet all the qualifications specified by the applicable regulatory requirement(s), and should provide evidence of such qualifications through up-to-date curriculum vitae and/or other relevant documentation requested by the Sponsor, the IEC/REB/IRB, and/or the regulatory authority(ies).

The investigator is responsible for ensuring that the clinical trial is performed in accordance with the protocol, current ICH guidelines on GCP, and applicable regulatory and local requirements.

GCP is an international ethical and scientific quality standard for designing, conducting, recording, and reporting studies that involve the participation of human subjects. Compliance with this standard provides public assurance that the rights, safety, and well-being of subjects are protected, consistent with the principles that originated in the Declaration of Helsinki, and that the clinical trial data are credible.

## **12.13 Financial Disclosure**

The investigator is required to disclose any financial arrangement during the clinical trial and for one year after, whereby the outcome of the clinical trial could be influenced by the value of the compensation for conducting the clinical trial, or other payments the investigator received from the Sponsor. The following information is collected: any significant payments from the Sponsor or subsidiaries such as a grant to fund ongoing research, compensation in the form of equipment, retainer for ongoing consultation or honoraria; any proprietary interest in investigational product; any significant equity interest in the Sponsor or subsidiaries as defined in 21 CFR 54 2(b) (1998).

## **12.14 Registration of Clinical Studies and Disclosure of Results**

The Sponsor or designee will register and/or disclose the existence of and the results of clinical trials as required by law.

## **12.15 Publication and Disclosure Policy**

As is customary for multicenter trials, publication by individual clinical sites or investigator/institution will not be allowed without the explicit written permission of the Sponsor. The Sponsor will determine authorship of the principal clinical trial manuscript(s) in conjunction with the investigators, in abiding with current guidelines and requirements of medical journals. For such manuscript(s), masthead roles for investigators will be determined based on subject enrollment and scientific contributions to the clinical trial.

# **13 RETENTION OF RECORDS**

The investigator agrees to adhere to the document retention procedures by signing the protocol. Essential documents, as listed below, must be retained by the investigator for as long as required by national and international regulations. The Sponsor will notify the investigator(s)/institution(s) when the clinical trial-related records are no longer required.

Essential documents include but are not limited to:

- IRB/REB/IEC approvals for the clinical trial protocol and all amendments
- All source documents and laboratory records

- CRF copies
- Subjects' informed consent / assent forms (with clinical trial number and title of trial)
- FDA form 1572
- Any other pertinent clinical trial documents

All source documents (e.g., informed consent forms, laboratory reports, progress notes, medical histories, physical and diagnostic findings, IP dispensing/disposition records) that support data in the CRFs of each subject must be retained in the files of the responsible investigator.

According to ICH guidelines for GCP, essential documents should be retained for a minimum of two years after the last approval of a marketing application in an ICH region and until there are no pending or contemplated marketing applications in an ICH region or at least 2 years have elapsed since the formal discontinuation of clinical development of the investigational product. However, these documents should be retained for a longer period (25 years) if required by relevant regulatory or legal authorities.

If the responsible investigator retires, relocates or for any other reason withdraws from the responsibility of keeping the clinical trial records, custody must be transferred to a person who will accept the responsibility. The Sponsor representative must be notified in writing of the name and address of the new custodian, prior to the transfer.

No records should be disposed of without written approval of the Sponsor.

1. INTRODUCTION

This statistical analysis plan is designed to outline the statistical methods for protocol ADX-102-AC-017:

“The INVIGORATE Trial: A single-center, randomized, double-masked, crossover design, vehicle-controlled, Phase 3 clinical trial to assess the efficacy and safety of reproxalap ophthalmic solution (0.25%) compared to vehicle in subjects with seasonal allergic conjunctivitis using the environmental exposure chamber (EEC)”

This document has been prepared based on protocol amendment version 6.0 dated 24 March 2021

2. STUDY DESIGN

2.1 OVERVIEW OF STUDY DESIGN

[figure not shown]
The double-masked, vehicle-controlled, randomized, two-way crossover clinical trial allows for the testing of Reproxalap Ophthalmic Solution (0.25%) versus Vehicle Ophthalmic Solution in subjects with ragweed-induced allergic conjunctivitis in the Environmental Exposure Chamber (EEC).

The clinical trial consists of four visits to the clinic (one Medical Screening visit, one Screening EEC visit, and two EEC treatment visits). The EEC sessions will be separated by an approximate two-week washout period to ensure adequate elimination of responses caused by allergen exposure in the EEC and allow the recuperation of mast cells.

The EEC clinical research facility is a room designed with the capacity and control mechanisms to expose participants to airborne ragweed pollen grains and maintains target temperature and relative humidity throughout.

The controlled pollen challenge, over time, allows evaluation of subject responses at any time-point throughout the challenge process.

Figure 1: Study Design

[figure not shown]
Eligible subjects will be randomized 1:1 to one of two treatment sequences of AB or BA where:

- Treatment A: Reproxalap Ophthalmic Solution (0.25%)
- Treatment B: Vehicle Ophthalmic Solution [REDACTED]

Approximately 126 subjects (approximately 63 per treatment sequence) will be enrolled and will follow the schedule for assessments (Table 1).

Table 1: Schedule of Events and Assessments

[REDACTED]

At the **Medical Screening Visit (Visit 1)**, subjects will undergo the informed consent process, and information about demographics, baseline characteristics, medical history, social history, physical examination will be performed and concomitant medication will be collected. Vital signs and samples for standard clinical safety laboratory tests will be obtained. A urine pregnancy test will be administered to women of childbearing potential (WOCBP).

Subjects will undergo ophthalmic examinations (Snellen VA, SLE, NCT, and a dilated fundus examination) to ensure initial eligibility criteria are met. A skin prick test for a panel of test allergens will be conducted; results must be positive (i.e., a wheal that is 3 mm greater than the negative control) for at least one test allergen and must include ragweed in order to proceed to Visit 2.

At all EEC sessions, assessments of ophthalmic evaluations will be collected [REDACTED]. [REDACTED]. In the event of an [REDACTED] failure, paper diary cards will be used as a back-up to collect symptom scores. For subject-reported symptoms of ocular itching, a standard 9 point (i.e., 0-4 with 0.5 unit increments) scale will be employed. For staff-assessed grading of conjunctival redness, a standard 9-point (i.e., 0-4 with 0.5 unit increments) will be employed. [REDACTED]

[REDACTED]

At the **EEC Screening Visit (Visit 2)**, qualified site staff will update concomitant medications and collect AEs, as applicable and perform tests for vital signs. A urine pregnancy test will be administered to WOCBP. Fundus exam, Snellen VA, SLE, subject rating of symptoms, and staff grading of conjunctival redness will be performed to ensure the anterior segment of the eye is healthy. [REDACTED]

Visit 2 Pre-EEC entry (Baseline):

- 1) Subject assessment for ocular itching and tearing will be recorded [REDACTED], and [REDACTED]
- 2) Staff-assessed conjunctival redness will be recorded [REDACTED].

Visit 2 Post-EEC entry:

- 1) Subject assessment for ocular itching and tearing will occur [REDACTED].
- 2) Staff-assessed conjunctival redness will be recorded [REDACTED].

[REDACTED]

At the **Randomization/Treatment EEC Session One (Visit 3)**, qualified site staff will update concomitant medications, collect AEs, as applicable and collect vital signs. A urine pregnancy test will be administered to WOCBP. Ophthalmic evaluations will be conducted (Fundus exam, Snellen VA, NCT SLE, subject rating of symptoms, and staff grading of conjunctival redness). [REDACTED]

Subjects will be randomized to receive a first dose of either Reproxalap Ophthalmic Solution (0.25%) (Treatment A) or Vehicle Ophthalmic Solution (Treatment B). Qualified site staff will instill one drop of the randomized treatment into each eye at approximately time zero [REDACTED] prior to entry to the EEC after all the pre-EEC assessments are done.

Visit 3 Pre-EEC entry (Baseline):

- 1) Subject assessment for ocular itching and tearing will be recorded [REDACTED] and [REDACTED]
- 2) Staff-assessed conjunctival redness will be recorded [REDACTED].

Visit 3 Post-EEC entry:

- 1) Subject assessment for ocular itching and tearing will occur [REDACTED].
- 2) Staff-assessed conjunctival redness will be recorded [REDACTED].

At approximately 90-minutes post-EEC entry (and after subject assessed itching and tearing and staff assessed conjunctival redness for all time-points post first dose have been completed), a second dose (one drop in each eye) of the same randomized treatment will be administered in each eye by the qualified site staff. [REDACTED]

Visit 3 Post-EEC exit (starting at approximately t = 215 minutes):

- 1) Subject assessed ocular itching and tearing will continue [REDACTED].
- 2) Staff assessed conjunctival redness will continue to be recorded post-EEC exit [REDACTED].

Subjects will be asked to return in at least two weeks for Visit 4.

At the **Treatment EEC Session Two (Visit 4)**, all procedures performed at Visit 3 will be repeated except that each subject will be given a different treatment dependent on the treatment sequence the subject was randomized to [Reproxalap Ophthalmic Solution (0.25%) (Treatment A) or Vehicle Ophthalmic Solution (Treatment B)].

Before EEC entry, a urine pregnancy test will be administered to WOCBP.

Subjects will undergo ophthalmic examinations (Snellen VA, SLE, NCT, and a dilated fundus examination), clinical safety lab tests and vital signs will be collected to ensure safety prior to exit of the clinical trial.

2.2 Sample Size

Approximately 670 subjects with ragweed-induced, moderate-to-severe allergic conjunctivitis will be screened in the EEC in order to randomize approximately 126 subjects, and for 100 subjects to

complete the study. Approximately sixty-three (63) subjects will be assigned to each of two (2) treatment sequences, AB and BA.

2.3 Randomization and Masking

2.3.1 Randomization

Eligible subjects will be randomized 1:1 to one of two treatment sequences of AB or BA where:

- Treatment A: Reproxalap Ophthalmic Solution (0.25%)
- Treatment B: Vehicle Ophthalmic Solution [REDACTED]

Approximately 126 subjects (approximately 63 per treatment sequence) will be enrolled.

Each subject screened for the clinical trial will be assigned a unique subject number that will be used to identify the subject throughout subject participation in the clinical trial. If a subject fails to be randomized, the reason should be documented in the source documents and case report form (CRF). The subject will be considered a screen failure.

2.3.2 Masking

Investigators, qualified site personnel, and subjects will be masked to the investigational product (IP) administered. The Sponsor will also be masked to the IP administered until database lock.

3. STUDY OBJECTIVES AND ENDPOINTS

3.1 Primary Objective

- To evaluate the efficacy and safety of Reproxalp Ophthalmic Solution (0.25%) compared to Vehicle Ophthalmic Solution for the treatment of allergic conjunctivitis using the EEC clinical trial design

3.2 Endpoints Assessment

3.2.1 Clinical Trial Assessments and Endpoints

- Ocular itching rated by the subject [REDACTED] using a 9-point, discrete, 0-4 scale with 0.5 increments
- Tearing rated by the subject [REDACTED] using a 4-point discrete 0-3 scale
- Ocular redness in the nasal and temporal conjunctiva separately in both eyes, based on a [REDACTED] descriptive and photographic scale from 0-4 with 0.5 steps

- Total Ocular Symptom Score (TOSS): composite score of ocular itching (0 – 4), ocular tearing (0 – 3) and ocular redness (0 – 4) with a maximum score of 11 units

3.2.2 Efficacy Endpoints

3.2.2.1 Primary Efficacy Endpoint

- Change from baseline in ocular itching score on a 9-point scale (0-4) from 110-210 minutes

3.2.2.2 Key Secondary Endpoint

- Change from baseline in conjunctival redness on a 9-point scale (0-4) during the chamber (approximately 12 to 212 minutes)

[figure not shown]
3.2.2.3 Secondary Endpoints

- Change from baseline in tearing on a 4-point scale (0-3) during the chamber (approximately 10 to 210 minutes)
- Change from baseline in TOSS on an 11-point composite score (sum of maximum score of itching, tearing and redness) during the chamber (approximately 10 to 212 minutes)
- Safety Endpoints
- Ophthalmic examinations
 - Snellen visual acuity (VA)
 - Slit lamp examination (SLE)
 - Non-contact intraocular pressure tonometry (NCT)
 - Dilated fundus examination at screening Visit 1 and at Visit 4
 - Undilated fundus examination at Visits 2 and 3
- Adverse events
- Vital signs
- Clinical laboratory tests

4. DEFINITIONS AND CONVENTIONS FOR DATA HANDLING

4.1 Definition of Baseline

For Safety evaluations, baseline is defined as the last non-missing value measured prior to initiation of study drug.

4.2 Handling of Missing Data

Generally, imputation of missing data will not be performed.

4.3 Unscheduled Visits for Safety Analysis

All unscheduled visit values will be excluded from summary tables but will be included on data listing.

4.4 Handling of Partial Dates for Medications

When determining prior or concomitant medications, partial start dates of prior and concomitant medications will be assumed to be the earliest possible date consistent with the partial date.

For the purposes of analysis, incomplete medication start dates and stop dates will be imputed.

- If a medication start date is incomplete, January will be imputed for missing month and/or the first day of the month will be imputed for missing day.
- If a medication stop date is incomplete, December will be imputed for missing month and the last day of the month will be imputed for missing day.
- If the imputed medication stop date is after the date of study completion, the date of study completion will be used instead.

4.5 Handling Partial Dates for Adverse Events

When determining the treatment emergent AE, partial dates will be handled as follows.

- If the day of the month is missing, the onset day will be set to the first day of the month unless it is the same month and year as first dose date. In this case, the onset date will be assumed to be the first date of treatment.
- If the onset day and month are both missing, the day and month will be assumed to be January 1, unless the event occurred in the same year as the study treatment. In this case, the event onset will be coded to the day of treatment to conservatively report the event as treatment-emergent.
- A missing onset date will be coded as the day of treatment. If the resulting onset date is after a reported date of resolution, the onset date will be set equal to the date of resolution.
- Imputation of partial dates is used only to determine whether an event is treatment-emergent; data listings will present the partial date as recorded in the eCRF.

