## **3 INVESTIGATIONAL PLAN**

### **3.1 Overall Clinical Trial Design and Plan**

[figure not shown]
The double-masked, vehicle-controlled, randomized, two-way crossover clinical trial allows for the testing of Reproxalap Ophthalmic Solution (0.25%) versus Vehicle Ophthalmic Solution in subjects with ragweed-induced allergic conjunctivitis in the EEC.

The clinical trial consists of four visits to the clinic (one Medical Screening visit, one Screening EEC visit, and two EEC treatment visits). The three EEC sessions (one EEC screening and two EEC treatment sessions) will be separated by an approximate two-week washout period to ensure adequate elimination of responses caused by allergen exposure in the EEC and allow the recuperation of mast cells, please refer to [Figure 6](#).

The EEC clinical research facility is a room designed with the capacity and control mechanisms to expose participants to airborne ragweed pollen grains and maintains target temperature and relative humidity throughout.

The use of the controlled EEC allergen exposure has been validated to provide spatial and temporal airborne allergen uniformity and to mimic the natural exposure on a peak allergen day.

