7.2 Adverse Events

AEs will be coded using the Medical Dictionary for Regulatory Activities (MedDRA) coding dictionary [REDACTED] preferred term (PT) and system organ classification (SOC).

An AE will be considered treatment emergent (TEAE) if it begins or worsens in severity after the first dose of the study drug through 30 days after the last dose of study drug, or the date of initiation of another investigational agent or surgical intervention.

Drug-related TEAEs are defined as definitely related, possibly related, or probably related to study drug. Any AEs with missing relationship to study drug will be considered as related to study drug.

All TEAEs with start dates prior to first dose date in Visit 4 EEC Treatment Session will be classified as AEs occurred in Visit 3 EEC Treatment Session.

An overall summary for number of subjects with events in each treatment will be provided including:

- Number of subjects with at least one TEAE
- Number of subjects with at least one Ocular TEAE
- Number of subjects with at least one drug-related TEAE
- Number of subjects with at least one drug-related Ocular TEAE
- Number of subjects with at least one serious TEAE
- Number of subjects with at least one serious Ocular TEAE
- Number of subjects with at least one TEAE leading to study discontinuation
- Number of subjects with at least one Ocular TEAE leading to study discontinuation

An AE is classified as an ocular AE if system organ class is coded as eye disorders.

The following types of summary for each treatment will be provided. Summaries will be sorted by decreasing frequency of PT within SOC which will be sorted alphabetically.

- TEAEs by SOC and PT
- Ocular TEAEs by SOC and PT
- Non-Ocular TEAEs by SOC and PT
- TEAEs by Casualty, SOC and PT

- Ocular TEAEs by Casualty, SOC and PT
- Non-Ocular TEAEs by Casualty, SOC and PT
- Serious TEAE by SOC and PT
- Ocular Serious TEAE by SOC and PT
- Non-Ocular Serious TEAE by SOC and PT
- TEAE by SOC, PT and maximum Severity
- Ocular TEAE by SOC, PT and maximum Severity
- Non-Ocular TEAE by SOC, PT and maximum Severity
- TEAEs leading to study discontinuation by SOC and PT
- Ocular TEAEs leading to study discontinuation by SOC and PT
- Non-Ocular TEAEs leading to study discontinuation by SOC and PT

If a preferred term or system organ class was reported more than once for a subject, the subject would only be counted once in the incidence for that preferred term or system organ class.

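### SAP 4.5 checks an imputed AE onset against the resolution date only when the whole onset date is missing, so some partly dated AEs that ended before the first dose become treatment-emergent

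*SAP*

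**What the plan says.** SAP 4.5 has three rules for an incomplete AE onset date.

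- **Day missing:** the rule reads "the onset day will be set to the first day of the month unless it is the same month and year as first dose date". For the exception: "In this case, the onset date will be assumed to be the first date of treatment".
- **Day and month missing:** 1 January of the recorded year, unless that is the year of treatment. In that case "the event onset will be coded to the day of treatment to conservatively report the event as treatment-emergent".
- **Whole date missing:** "A missing onset date will be coded as the day of treatment". The same bullet continues: "If the resulting onset date is after a reported date of resolution, the onset date will be set equal to the date of resolution".

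The section then limits the use of these dates: "Imputation of partial dates is used only to determine whether an event is treatment-emergent".

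SAP 7.2 defines a TEAE as an AE that starts, or becomes more severe, once dosing has begun. It adds that TEAEs starting before the Visit 4 dose "will be classified as AEs occurred in Visit 3 EEC Treatment Session".

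Protocol 7.6 and 9 have AEs collected from the signing of consent. Protocol 3.1 says the three chamber sessions, including the screening session at Visit 2, "will be separated by an approximate two-week washout period". Study drug is first given at Visit 3.

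**The concern.** The check against the resolution date is written into one rule of three. The other two move the onset forward to the treatment day even when the record shows that the event was already over. Less information then gives the better answer: with no onset date the event is pulled back to its resolution and excluded, while with the correct month or year on file it is counted.

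Deciding treatment emergence is the only purpose SAP 4.5 gives these imputed dates, so the gap affects exactly the decision the rules exist to make. An affected event enters the TEAE tables under whichever product the subject received at Visit 3. If its causality field is also blank, SAP 7.2 counts it as drug-related as well.

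Events that end before dosing can occur. Collection starts at consent, and Visit 2 includes a pollen challenge and a drop administration about two weeks before the first dose.

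**Working it through.** The plan gives no figure to reproduce, so the check is to apply the three rules literally and see what they return.

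**Assumptions.** The dates are illustrative and not from the documents: first dose 20 March 2021, AE resolved 10 March 2021. The day of treatment is taken as the first-dose day. An imputed onset on that day counts as treatment-emergent; the second rule says so expressly, and the first is read the same way.

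**Results for the AE resolved on 10 March:**

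| Recorded onset | Imputed onset as written | TEAE? | Imputed onset with the check on every rule | TEAE? |
|---|---|---|---|---|
| Day missing, March 2021 | 20 March 2021 | Yes | 10 March 2021 | No |
| Day and month missing, 2021 | 20 March 2021 | Yes | 10 March 2021 | No |
| Wholly missing | 10 March 2021 | No | 10 March 2021 | No |
| Day missing, February 2021 | 1 February 2021 | No | 1 February 2021 | No |
| Day and month missing, 2020 | 1 January 2020 | No | 1 January 2020 | No |

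In the first two rows the imputed onset falls 20 − 10 = 10 days after the event's own end. Both events start before the Visit 4 dose, so SAP 7.2 assigns them to the Visit 3 session.

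**Does extending the check lose any event that could have followed dosing?** The five onset patterns were rerun with resolution on 20 March, on 25 March, and missing. In all 15 cases (5 × 3) the classification is the same with and without the wider check. Only the first two rows of the table change.

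**When could such events arise?** Visit 1 is 2 days to 8 weeks before Visit 2 (Protocol synopsis, Study Design), and Visit 3 follows Visit 2 by about 2 weeks. The time from consent to first dose is thus about 2 + 14 = 16 days to 56 + 14 = 70 days. Protocol 9.1.1.1 treats conditions present before Visit 2 that do not worsen as baseline conditions, so the main window is the two weeks or so between Visits 2 and 3.

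**The case against.** **The check may have been meant for all three rules.** It comes after all of them, and its reference to the resulting onset date could be read as the output of any one. That reading is possible, but the sentence sits inside the bullet for a wholly missing date and nothing elsewhere in either document extends it. Two programmers could derive different TEAE counts in good faith, which is itself a reason to settle the text.

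**The rule is deliberately conservative.** The second rule says so. Conservatism is reasonable while it is unknown whether the event began before or after dosing. A recorded resolution before the first dose removes that doubt, and the third rule shows that its authors accept this.

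**Affected events should be rare.** This stands. An event needs a partial onset date, a known resolution before dosing, and a match to the first-dose month or year. Protocol 9.1.1.3 asks for start and end dates and times, Protocol 12.6 requires full source verification, and staff collect AEs at Visits 2 and 3.

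**The tables are descriptive and the listings transparent.** This also stands. SAP 7.2 plans counts without tests, all AEs are listed, and listings show the date as recorded, so a careful reader could spot a case.

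A reader might try to infer a misclassification rate from the calendar. If Visits 2 and 3 are 14 days apart and visit dates are spread evenly, they share a month in (30.4 − 14)/30.4 = 54% of subjects. A gap of 17 days gives 44% and one of 21 days gives 31%. The documents give no visit dates, and these shares say nothing about how often an onset day is missing. They are not an error rate.

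**Conclusion.** The point holds within stated limits. As written, SAP 4.5 makes an AE with a recorded pre-dose resolution treatment-emergent when (a) only the onset day is missing and the month and year match the first dose, or (b) day and month are missing and the year matches the treatment year. The event is then charged to the Visit 3 product. This is a stated rule giving a wrong result, not merely missing detail.

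Two stronger readings are not supported:

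- **Every partly dated AE that ended before dosing is affected.** It is not. Day-missing onsets in an earlier month, and onsets in an earlier year, are imputed before dosing and correctly excluded.
- **The comparison between products is biased.** These events end before any product is given, and randomization to sequence takes place at Visit 3, so the expected number of false events is the same under both products. The error is towards over-reporting. Efficacy analyses are untouched.

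The size in this trial cannot be computed, because the documents give no count of partly dated AEs; it is probably small. The conclusion rests on the literal placement of the resolution check and on reading an imputed onset on the first-dose day as treatment-emergent. This is a minor point, worth correcting because the correction is so cheap.

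**What to change.** Take the resolution check out of the third bullet and make it a separate rule for every imputed onset. Suggested text: *Where any imputed onset falls later than the reported resolution date, the resolution date is used as the onset. An AE with a complete reported resolution date before the first dose is not treatment-emergent.*

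SAP 4.5 has no rule for incomplete AE resolution dates, so add one clause: AEs that resolve on or after the first dose, or whose resolution date is absent or incomplete, keep the present conservative handling, unless the known part of the resolution date already places it before the first dose.

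The cost is a sentence or two in the SAP and a minor change to the AE derivation program, made before database lock. In the cases checked, no event that could have followed dosing is lost.
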